Analysis Plan for Hypotheses 1 and 2: We will apply mixed effect models to evaluate differential changes in weight measures at 6, 12, 18, and 24 months from baseline, with fixed terms of group (DPP Plus vs. DPP Minimal), time as a factor (6,12,18, and 24 months), and the group by time interaction. We will employ the following steps as the pre-randomization balancing logic: (1) group subjects by weight loss status (≤ 3.5 vs. > 3.5 percent at 6-months) and age (≤ 70 vs. > 70 years at baseline), (2) group subjects by sex (male vs. female) and race (Black/African American or Black/Mixed/Other vs. White/Caucasian), (3) group subjects using all 4 factors (based on 2x2 frequency table) and (4) randomly assign the subjects in the same cell into 2 conditions (DPP Plus vs. DPP Minimal). Subject will be included as a random term. To test the differential treatment effect, we will evaluate the coefficients that are associated with the group and the group by time interaction by using an F test. Planned contrasts will be set up from the mixed models to compare the improvement in weight from baseline to Months 12, 18 and 24 between the two conditions (DPP Plus vs. DPP Minimal). A generalized mixed-effect model will be fit to the binary outcome of achieving $\geq 5\%$ weight loss at 6, 12, 18, and 24 months, with the logit link, which includes similar fixed and random terms as above. Average percent weight loss and the proportions achieving $\geq 5\%$ weight loss will be compared between the two groups at 12, 18 and 24 months. We will perform similar analyses for fasting glucose, HbA1c, and insulin (and other biometric measures), physical activity/function, and secondary outcomes at subsequent assessment points.

The planned contrasts will be set up to compare differential changes from baseline to Months 12, 18, and 24. Benjamini-Hochberg's method will be used to control for the overall type I error for multiple secondary outcomes. More intensive modeling will be performed accounting for factors that are known to affect the outcomes as well as those that have been found to differ between treatment conditions at baseline and at Month 6 (the timepoint at which participants are stratified by $<$ or $\geq 3.5\%$ weight loss and other factors and randomly assigned to the two 18-month conditions). We will also perform analyses in which we restrict our linear and generalized

mixed-effect analyses to those who did not reach $\geq 5\%$ weight loss at 6 months and set up the contrasts to compare DPP Plus with DPP Minimal, on average, and the proportion reaching $\geq 5\%$ at 12 months and 18 months from baseline.

Exploratory Aim: Examine available Medicare data for those insured by a large regional payer to assess group and time from baseline differences in medical utilization metrics (e.g., type of outpatient, inpatient, or emergency visits) and participation in activity programs, for a proportion of the sample. We will extract Medicare data on numbers of outpatient, inpatient and emergency visits, and number of subjects participating in activity programs, and compare the numbers between the two conditions using linear and generalized regression models. We will explore the potential moderation effects of sex and race. We will include the interaction of sex by group or race by group in the aforementioned mixed-effect models, as well as the three-way interaction of sex, group and time or race, group and time, if the group by time interaction is significant in the original model.

Power and Sample Size Considerations. We powered this study on the main comparisons between the Active Comparator: DPP Plus 30-minute Calls (DPP Plus) and the Placebo Comparator: DPP Minimal 15-minute Calls (DPP Minimal) on average weight loss at 12 months from baseline. With 180 subjects per arm and projected 90% attritions at Months 12, we would have 80% power to detect effect sizes of 0.31, using two-sided t tests at the 0.05 level. Our prior Pitt Retiree study observed approximately 7.5 % weight reduction at 12 months among those subjects who received active intervention for 12 months, and 5.5% reduction at 12 months among those in the placebo comparator group. Assuming similar effects and similar standard deviation of 5.8% as observed in the Pitt Retiree study, we expect to see a standardized group difference ranging 0.34 at Months 12 between DPP Plus and DPP Minimal. We anticipate that our projected sample size will enable us to detect group differences with power greater than 0.8 for our primary weight outcome.

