Aim 1: Document the impact of DPP-BI compared to DPP-MS on weight at 12, 18, and 24 months.

Hypothesis 1: Overall, DPP-BI compared to DPP-MS will result in more favorable weight loss (average change and the proportion reaching $\geq 5\%$) at 12, 18, and 24 months.

Aim 2: Document the impact of DPP-BI compared to DPP-MS on cardiometabolic, physical activity/function, secondary outcomes, and behavioral adherence measures at 12, 18 and 24 months.

Hypothesis 2: Overall, DPP-BI compared to DPP-MS will result in more favorable cardiometabolic, physical activity/function, secondary outcomes, and behavioral adherence measures at 12, 18, and 24 months.

Reducing cardiometabolic risk and promoting functional health in community-based elders with obesity and pre-diabetes: evaluating sustainable follow-up strategies

Exploratory Aim: We will examine differences in intervention response (weight, cardiometabolic, and function) by race (African American, Caucasian). For a proportion of the sample, we will explore Medicare data for group differences in medical utilization (medications, outpatient, inpatient, emergency visits) and participation in activity programs.

Evaluating incremental refinements to standard DPP approaches through community centers providing aging services, in alignment with MDPP^{1,37} and other Medicare subsidized activity benefits, will improve our understanding of the most effective and potentially sustainable long term approaches for weight control and health maintenance in vulnerable older adults. A successful demonstration of 12-, 18- and 24-month interventions using video- and telephone-coaching strategies to sustain weight loss self-management and enhance behavioral activation for cardiometabolic control and functional health outcomes would have significant individual and public health benefit.

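### The supplementary analysis of those below 5% loss at Month 6 keeps Month 6, the selecting visit, among its responses and names contrasts only at 12 and 18 months

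*SAP*

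**What the plan says.** **Main models** (SAP, Analysis Plan for Hypotheses 1 and 2; same in Protocol 18.0). The linear model has time as a factor at 6, 12, 18 and 24 months. On the covariance the SAP says only "Subject will be included as a random term". The binary model is for reaching 5% "weight loss at 6, 12, 18, and 24 months, with the logit link, which includes similar fixed and random terms as above". The planned contrasts "compare the improvement in weight from baseline to Months 12, 18 and 24 between the two conditions".

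**Restricted analysis** (SAP, same section; Protocol 18.0). The linear and generalized models are restricted to those below 5% "weight loss at 6 months and set up the contrasts to compare DPP Plus with DPP Minimal, on average, and the proportion reaching" 5% "at 12 months and 18 months from baseline". Neither document says that Month 6 leaves the responses or becomes a covariate. Further modelling adjusts for known prognostic factors and for "those that have been found to differ between treatment conditions at baseline and at Month 6", so a Month-6 covariate is not clearly fixed in advance.

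**Timing.** Protocol 4.0 makes 24 months the primary endpoint and places randomization at the six-month assessment. Protocol 6.0 says Wave 6 (planned 40 of 360) stopped at 18 months, while the note to Table 2 still schedules its 24-month visit. These two statements need reconciling.

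**The concern.** Month 6 is measured before randomization and defines who is in the subset. It cannot carry a treatment effect, and its distribution in the subset is cut off at 5%. Left among the responses, it does two things. It gives the logit model a visit with no events in either arm. It also gives the linear model one visit with much less spread than the others, which lowers a pooled variance and makes the later tests too liberal.

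This is the only analysis in the plan devoted to people who missed the target by Month 6, a group that Protocol 2.0 singles out. It also has no clearly planned contrast at the primary time point. The fitted model could supply a 24-month estimate, but reporting it, or not, would then look like a choice made after seeing the data.

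**Working it through.** **1. The plan's own figure.** The documents give no size or power for this subset. For the whole sample: 180 x 0.90 = 162 per arm, d = 0.31, and 0.31 x sqrt(162/2) = 2.79. Power is Phi(2.79 - 1.96) = 0.797, which matches the stated 80%. It holds only if the stated 90% attrition is read as 90% retention.

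**2. Subset size (assumed).** Retention at 6 months is 90% (SAP), so 0.90 x 360 = 324. If 37% fall below 5%, the subset is 0.37 x 324 = 120. The 37% is the complement of the 63% in Protocol 2.0, a 12-month figure from an earlier program, so 60% is also shown.

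**3. Logit model.** By selection the Month-6 outcome is 0 for everyone in both arms, so the Month-6 intercept and group term have no finite maximum-likelihood estimate. In four simulated data sets (153 to 193 people) the Month-6 intercept ran to between -24 and -43. The 12-month group estimate and the random-intercept SD were the same with and without Month 6 (for example -0.95 and 3.39 both ways). Convergence in SAS was not tested.

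**4. Linear model, equal later variances.** Take Month-6 loss as normal with SD 5.8 (SAP).
- P(below 5%) = 0.37 gives a = -0.332 and mean 5 + 0.332 x 5.8 = 6.92.
- lambda = phi(a)/Phi(a) = 1.020. The variance factor is v = 1 - a x lambda - lambda^2 = 0.297, so the Month-6 SD is 5.8 x sqrt(0.297) = 3.16.
- Later SD in the subset is 5.8 x sqrt(1 - r^2(1 - v)), where r is the assumed correlation with Month 6.
- With complete data, a random-intercept model with one residual variance uses the mean of the four visit variances for every visit. So model SE / true SE = sqrt(mean of four variances / later variance), and type I error = 2 x Phi(-1.96 x ratio).

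| r | Later SD | SE ratio | Type I, Month 6 kept | Month 6 dropped |
|---|---|---|---|---|
| 0.50 | 5.27 | 0.917 | 7.2% | 5.0% |
| 0.75 | 4.51 | 0.934 | 6.7% | 5.0% |
| 0.85 | 4.07 | 0.949 | 6.3% | 5.0% |

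With 60% below 5%, the ratios are 0.935 to 0.965 and type I error is 5.9-6.7%. Simulation with complete data and n = 100 to 160 gave 6.1-7.6% kept and 4.7-5.5% dropped. Mean estimates of a 2.0-point effect were 1.97-2.01 in every setting.

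**5. Linear model, variance rising over time.** With SD factors 1, 1.1, 1.2 and 1.3 at Months 6, 12, 18 and 24, r = 0.75 and 37% below 5%:

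| Visit | Month 6 kept | Month 6 dropped |
|---|---|---|
| 12 | 5.0% | 3.2% |
| 18 | 7.3% | 4.9% |
| 24 | 9.8% | 7.0% |

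A separate simulation with correlations falling from 0.85 to 0.65 gave 4.5% kept and 3.4% dropped at Month 12, and 8.4% and 6.9% at Month 24.

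**6. Month-6 change as a covariate.** Assume the plan's 2.0-point difference applies at Month 24. The number left is 120 x (0.80/0.90) x (320/360) = 95. SE = SD x sqrt(4/95) and power = Phi(2.0/SE - 1.96). With the covariate, the SD becomes 5.8 x sqrt(1 - r^2).

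| r | SD without / with | Power without / with |
|---|---|---|
| 0.50 | 5.27 / 5.02 | 46% / 49% |
| 0.75 | 4.51 / 3.84 | 58% / 72% |
| 0.85 | 4.07 / 3.06 | 67% / 89% |

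In simulated logistic fits at Month 24 the gain was small: 28.8% to 33.0% (r = 0.5) and 42.5% to 46.5% (r = 0.75) with n = 95. With n = 120 it was 40.6% to 40.5% and 48.7% to 53.9%.

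**7. Joint test.** If the main group and group-by-time test were carried over, the empty Month-6 term adds a degree of freedom. At noncentrality 10.903, power falls from 80.0% (3 df) to 75.8% (4 df).

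**The case against.** **The error rate is not a property of the written plan.** The SAP gives a random subject term and no residual structure. With visit-specific variances, the truncated visit would not be pooled with the others. A reader might infer that the plan as written tests at 6-8%; the documents do not support that, because the figure needs a common residual variance and equal later variances. This objection stands. Step 5 also shows that dropping Month 6 does not by itself restore 5%: Month 12 becomes conservative and Month 24 stays liberal.

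**The logit defect reaches no named contrast.** This stands too. The damage is confined to the Month-6 terms, possible convergence trouble, and a joint test that the restricted text does not mention.

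**The 24-month gap is partly wording.** The visits in "at 12 months and 18 months from baseline" may modify only the proportion, and the contrasts may be the Month 12, 18 and 24 set named earlier in the same paragraph. Elsewhere the plan pairs the mean with the proportion, as in "Average percent weight loss and the proportions achieving" (SAP) and "more favorable weight loss (average change and the proportion reaching" (Protocol 2.0), so *on average* most naturally means mean weight loss at each visit. That leaves an ambiguity to settle; it does not prove that 24 months was meant to be excluded. The Wave 6 stop could explain an omission, but the SAP does not say so, and the main analysis keeps its 24-month contrast despite the same stop.

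**The covariate is a preference.** It corrects no error; it is a gain in precision.

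**Conclusion.** The point holds, and it is minor because the analysis is supplementary. As written, a pre-randomization visit that selects the subset stays among the responses, and 24 months is not clearly among the contrasts.

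If one residual variance is used and 37-60% fall below 5%, the later standard errors are about 4-8% too small with equal later variances. Single-visit type I error is then about 6-7.5%. If variance grows over time, the error differs by visit. The subset share, the correlations and the variance pattern are assumptions; the documents give none of them.

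Two stronger inferences are not supported. One is that selecting on Month 6 biases the arm comparison: the subset is fixed before randomization, so it is valid and its point estimates are unbiased. It is not a randomization stratum, since the SAP balances at 3.5%. The other is that the main result is compromised: the whole-sample primary analysis does not use this restriction.

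**What to change.** In the restricted analysis of the SAP and Protocol 18.0:

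- Use only Months 12, 18 and 24 as responses in both the linear and the logit model.
- Include continuous Month-6 percent weight change as a covariate fixed in advance, whether or not the arms are found to differ at Month 6.
- Allow visit-specific residual variance in the linear model, for example with an unstructured within-person covariance.
- Say that *on average* means mean percent weight loss at each visit.
- Name the 24-month contrast, or state that it is omitted because Wave 6 ended at 18 months. Reconcile that statement with the note to Table 2.

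The cost is a few sentences and a few lines of code. No new data are needed.
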